### Multiple Evaluations within the Same Analysis Window

After all the observations have been slotted based on the table above, if there are multiple valid observations for an assessment within an assigned analysis visit window, only 1 of these observations will be used for summary statistics and analyses. The observation to be used is determined using the following hierarchy (in decreasing order):

- The observation closest to the target study day
- The later observation if 2 observations are equally close to the target study day

For missing values where the LOCF algorithm is applied, it is always the last valid observation on treatment carried forward, even though this might not be the observation obtained by the above hierarchy and used in the summaries by visit window.

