3.3.2.2 Vital Signs

Vital signs will be assessed at Screening, Baseline, and each subsequent study visit or ET.

Vital signs measured will include blood pressure (systolic and diastolic), HR, respiratory rate

(RR), temperature, and weight. Height will be assessed at Screening only. Vital signs must be assessed following at least 5 minutes of rest (sitting) to ensure accurate measurement. No other measurements or procedures should be performed during this 5-minute period. When possible, vital signs should be collected prior to the 6MWT. If vital signs cannot be obtained prior to the 6MWT, they should be obtained after recovery of the 6MWT. Vital signs should also be assessed in the case of abnormal clinical signs and symptoms.

3.3.2.3 12-Lead Electrocardiogram

A 12-lead ECG will be recorded after at least 5 minutes of rest in the semi-recumbent position at Baseline (prior to study drug) and repeated at the Week 16 or ET Visit. Recordings should include lead II as a rhythm strip and contain at least 5 QRS complexes. ECG parameters to be collected include rhythm, HR, PR interval, QT interval, QRS duration, and any clinically significant abnormalities.

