15.2 GUIDELINES AND DEFINITIONS FOR RECORDING ADVERSE EVENTS

The Investigator or a designated member of his/her staff will probe each subject for any AEs that may have occurred. The Investigator should always ask the same question when conducting the verbal probe in order to ensure uniformity between subjects. The Investigator should ask:

"How are you doing (feeling)?"

Based on the subject's response to this question, the Investigator should ask additional questions relevant to the specific complaint such as:

"How severe is/was the symptom?"

"How often did the symptom occur?"

"How long did the symptom last?"

It is the Investigator's responsibility to review the results of all diagnostic and laboratory tests as they become available and ascertain if there is a clinically significant change from Baseline. If the results are determined to be a clinically significant change from Baseline, this should be reported as an AE. The Investigator may repeat the diagnostic procedure or laboratory test or request additional tests to verify the results of the original tests. When possible, a diagnosis associated with the abnormality should be used as the reported AE.

Using provided definitions, the Investigator will then:

(1) rate the intensity and seriousness of the AE, (2) estimate the causality of the AE to study drug, and (3) note actions taken to counteract the AE.

Definitions of Intensity, Seriousness, Causality, Action Taken, and Outcome

INTENSITY

An assessment of the relative intensity (severity) of an AE is based on the Investigator's clinical judgment. The maximum intensity encountered during the evaluation period should be checked. The assessment of intensity should be independent of the assessment of the seriousness of the AE.

SERIOUSNESS

A serious AE is one that represents an actual or potential significant hazard. This includes, but is not limited to, an event that is fatal, life-threatening, permanently or severely disabling, requires or prolongs inpatient hospitalization*, is a congenital abnormality (offspring of subject) or is medically significant (important medical events that may not result in death, be life-threatening, or require hospitalization may be considered an SAE when, based upon appropriate medical judgment, they may jeopardize the subject and may require medical or surgical intervention to prevent 1 of the outcomes listed in this definition).

*Hospitalizations that would not be considered SAEs include those for:

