### 8 GENERAL CONSIDERATIONS FOR DATA ANALYSES

All the data collected in the electronic Case Report Form (eCRF) will be listed. In general, listings will be sorted by treatment group, subject number, and scheduled assessment (if applicable). Listings will include assessment date, assessment time (if available), study day, and all relevant data collected in the eCRFs. For data collected on a fixed schedule, the assessment identifier or the nominal time point will also be included on the listing. Repeat or redundant observations within an assessment window and observations that do not fall within any predefined assessment window (and will, therefore, be excluded from summaries) will be flagged in these listings. Subjects who are not to be included in the analysis population (eg, Safety population, Per-protocol population) will be flagged.

In general, the data will be summarized by scheduled assessment (if applicable) within each treatment group. For continuous variables, summary statistics will include the mean, standard deviation, median, minimum, and maximum. For summaries of non-normal data such as 6MWD, interquartile range (lower quartile, upper quartile) may also be included. Minimums and maximums will be expressed using the level of precision in which the variable was collected. All other statistics will be rounded, using an additional decimal place than was collected. For discrete variables, summaries will include the frequency and percentage in each category. Percentages will be rounded to 1 decimal place. For all inferential analyses and descriptive comparisons, p-values will be rounded to 4 decimal places. Values less than 0.0001 will be denoted as <0.0001, and values greater than 0.9999 will be denoted as >0.9999 whenever practical, categories of discrete variables will be ordered and labelled as they appear in the eCRF, and all categories represented on the case report form will be included in summaries, even when they do not apply to any subjects in the study.

Unless otherwise specified, all statistical tests will be 2-sided at alpha level 0.05. All statistical calculations will be completed using SAS® Version 9.4 or above.

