### 8.6 ASSESSMENT WINDOWS

For any data summarized by scheduled visit, an analysis visit window will be used. The scheduled visits, as recorded on the eCRFs, and the corresponding target days and study day intervals are specified in Table 8-4. The analysis visit window will be derived based on the information specified in Table 8-4.

In the protocol, the visit window for Week 4, Week 8, Week 12, and Week 16 is  $\pm 5$  days and the visit window for the Week 15 visit is  $\pm 5$  days and at least 24 hours prior to Week 16 6MWT. In order to allow slotting of discontinuation visits and visits outside the planned schedule, the visit windows have been expanded for analysis purposes for Week 4, Week 8, Week 12, and Week 16. The nominal study visit identified as Week 15 in the eCRF will be used for the Week 15 visit provided it is at least 24 hours prior to Week 16 6MWT or there is no Week 16 visit.

Visit	Target Study Day	Study Day Interval
ECGs, SGRQ:		
Baseline	1	Study Day ≤1 (prior to the date of the first dose)
Week 16	113	1 < Study Day
PFTs, Clinical laboratory as	ssessments and NT-proF	BNP:
Baseline	1	Study Day $\leq 1$ (prior to the first dose)
Week 8	57	$1 < $ Study Day $\leq 71$
Week 16	113	99 < Study Day
Peak 6MWT:	·	
Baseline	1	Study Day ≤1 (prior to the first dose)
Week 4	29	$1 < $ Study Day $\leq 43$
Week 8	57	$43 < $ Study Day $\leq 71$
Week 12	85	$71 < $ Study Day $\leq 99$
Week 16	113	99 < Study Day
Trough 6MWT:		
Week 15	106	Nominal study visit and at least 24 hours prior to Week 16 6MWT or no Week 16 visit
Vital signs, Pulse oximetry:		
Baseline	1	Study Day $\leq 1$ (prior to the first dose)
Week 4	29	$1 < $ Study Day $\leq 43$
Week 8	57	$43 < $ Study Day $\leq 71$
Week 12	85	$71 < $ Study Day $\leq 99$
Week 15	106	Nominal study visit and at least 24 hours prior to Week 16 6MWT or no Week 16 visit
Week 16	113	99 < Study Day

 Table 8-4
 Assessment Windows for Scheduled Visits

Note: Study Day = (Assessment Date) - (First Dosing Date) +1

Abbreviations: 6MWT, 6-Minute Walk Test; ECG, Electrocardiogram; NT-proBNP, N-Terminal pro-brain natriuretic peptide; PFT, Pulmonary function test.

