# 12.5.1 Clinical Chemistry

The following clinical chemistry parameters will be evaluated by the central laboratory:

Parameter	Units
Sodium	mmol/L
Potassium	mmol/L
Bicarbonate	mmol/L
Chloride	mmol/L
Total bilirubin	umol/dL
Alkaline phosphatase	U/L
Alanine aminotrasferase	U/L
Aspartate aminotransferase	U/L
Urea nitrogen	mmol/dL
Creatinine	umol/L
Calcium	mmol/L
Albumin	g/L

Values that are "High" or "Low" with respect to the reference range provided by the central laboratory will be flagged with an "H" or an "L," respectively. All parameters will be listed for all subjects and assessments, along with their respective "High/Low" flags.

Values of these parameters at each visit, and their corresponding changes from Baseline will be descriptively summarized by treatment group.

For each parameter, the frequency and percentage of subjects within each treatment group who had "Low," "Normal," or "High" Baseline values, then subsequently had "Low," "Normal," or "High" follow-up values at each visit will be presented in a shift summary.

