### **12.6 OTHER SAFETY MEASURES**

#### 12.6.1 Electrocardiograms

All ECG assessments will be listed for all subjects. This listing will include the heart rate, the ECG interval from the beginning of QRS complex to end of the T wave (Q-T interval), the QT interval corrected for heart rate (QTc) (calculated using formulas by both Bazett and Fridericia as described in Section 8.4), the time between P wave and beginning of QRS complex in ECG (P-R interval), the electrocardiographic wave (QRS) duration, ECG results (Normal/Abnormal), whether there were clinically significant changes from Screening visit, whether abnormalities were present, and details and comments on any abnormalities. The ECG results at Baseline and changes at Week 16 will be descriptively summarized by treatment group. In addition, for QTc intervals calculated using both the Bazett and Fridericia methods, the number and percent of subjects with values  $\geq$ 500 msec and the number and percent of subjects with changes from Screening of <30 msec, 30 to <60 msec, and  $\geq$ 60 msec will be presented. Additionally, each abnormality will be summarized by number and percentage of subjects reporting at each visit by treatment group.

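### SAP 8.6's one-value-per-window rule has no safety exception, so laboratory shift tables, ECG abnormality counts and, on the natural reading, QTc counts can miss unscheduled or repeated on-drug abnormal values

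*SAP*

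**What the plan says.** **The rule.** SAP 8.6 opens with its scope: "For any data summarized by scheduled visit, an analysis visit window will be used". It also explains why the windows are wide: "In order to allow slotting of discontinuation visits and visits outside the planned schedule, the visit windows have been expanded for analysis purposes". Its subsection on multiple evaluations adds that "if there are multiple valid observations for an assessment within an assigned analysis visit window, only 1 of these observations will be used". The value kept is the one nearest the target day, and the later one if two are equally near.

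**The windows (SAP Table 8-4).** ECGs have one post-baseline window, everything after Day 1 with target Day 113. Laboratory tests and PFTs have two: Days 2 to 71 (target 57) and after Day 99 (target 113). SAP 8 says what happens to the rest: "observations that do not fall within any predefined assessment window (and will, therefore, be excluded from summaries". Those values are flagged in the listings.

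**The outputs.**
- Chemistry (SAP 12.5.1): Low/Normal/High "follow-up values at each visit will be presented in a shift summary". Hematology (SAP 12.5.2) is set out in the same way, by assessment.
- ECG (SAP 12.6.1): subjects at or above 500 msec and by size of change are counted "for QTc intervals calculated using both the Bazett and Fridericia methods", with no visit named. The next sentence counts abnormalities by visit.
- FEV1 (SAP 12.4): subjects with a fall of more than 20% at any post-baseline visit.

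**Extra measurements.** The protocol foresees them. Appendix 15.2 says: "The Investigator may repeat the diagnostic procedure or laboratory test". Section 3.3.2.4 has clinically significant laboratory abnormalities treated or followed until they are normal or acceptable.

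**The concern.** Picking one value per window is a sensible way to build a by-visit mean. It suits an outlier count or a shift table less well, because those tables exist to find extreme values. Here the rule meets two kinds of measurement that are not a random sample of a subject's readings: tests done because something looked wrong, and repeats done because the first result was abnormal. If the former lose to a routine value nearer the target, or the first result loses to its own repeat, the table misses an abnormality that did occur on drug.

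Protocol 3.3.2 makes treatment-emergent changes in laboratory values, ECGs and PFTs part of the primary assessment of safety, and Protocol 10.3.4 promises a comparison between arms. The tables used for that comparison are the ones affected.

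**Working it through.** The plan states no figure on this point, so the check applies Table 8-4 and the selection rule day by day.

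**Inputs.** Target days and windows are from SAP Table 8-4. The closest-then-later rule is from SAP 8.6. The visit window of ±5 days is from footnote b of the protocol's schedule (Section 3.2).

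**1. Unscheduled ECG with a Week 16 ECG done in window.** The scheduled tracing falls on Days 108 to 118, so it is at most 5 days from Day 113. An unscheduled tracing on Day d ≤ 107 is 113 − d ≥ 6 days away and always loses. Days 2 to 107 are 106 days, and the tracing is dropped on 106 of 106. On Days 109 to 118 the outcome depends on the day of the scheduled tracing.

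**2. Unscheduled laboratory value with scheduled values in window.** Days on which it can never count, within Days 2 to 107:

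| Days | Reason | Number |
|---|---|---|
| 2–52 | Never nearer Day 57 than a visit on Days 52–62, nor later on a tie | 51 |
| 63–71 | At least 6 days from Day 57 | 9 |
| 72–99 | In no window | 28 |
| 100–107 | At least 6 days from Day 113 | 8 |
| Total | | 96 of 106 |

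On the other 10 days (53 to 62) it can count, depending on the day of the Week 8 visit.

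**3. A repeat of a scheduled laboratory test.** Let o be the visit's offset from target (−5 to +5, 11 possible days) and k the days to the repeat. The repeat is chosen if |o + k| ≤ |o|, that is, if o ≤ −k/2.

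| Repeat after | Offsets where it replaces the first value | Visit days |
|---|---|---|
| 1–2 days | −5 to −1 | 5 of 11 |
| 3–4 days | −5 to −2 | 4 of 11 |
| 5 days | −5 to −3 | 3 of 11 |
| 7 days | −5, −4 | 2 of 11 |
| 10 days | −5 | 1 of 11 |

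If the first value is on or after the target day, it is kept. These are counts of permitted days. They become probabilities only if visits spread evenly over the window, which is an assumption.

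**4. The Day 72–99 gap.** As printed, the Week 8 window closes at Day 71 and the Week 16 window opens after Day 99, so 99 − 72 + 1 = 28 days are uncovered. This does not need an unscheduled test. Protocol 7.6 places laboratory tests and PFTs at the early termination visit, if possible before drug is stopped, and such a visit on Days 72 to 99 gives on-drug values that SAP 8 removes from every summary, including the count of FEV1 falls over 20%.

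**5. Direction.** A count of subjects whose selected value is abnormal cannot exceed the count with any abnormal on-treatment value, since the selected values are a subset. Relative to that question the rule can only under-count.

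**The case against.** **QTc scope.** SAP 8.6 confines the windows to data summarized by scheduled visit, and the QTc counts name no visit although the next sentence does. This stands in part: the scope is inferred. With one post-baseline ECG window and one value per window, the inference is the natural one, and silence on an outlier count is itself a gap.

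**Unscheduled tests may be few.** ECGs are planned only at Baseline and Week 16 or early termination, and no for-cause PFT is named. This stands as a limit on size. It does not answer the 28-day gap, which catches early termination visits.

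**Other safeguards.** Clinically significant laboratory values and diagnostic changes are reported as adverse events (Protocol 3.3.2.4 and 15.2) and summarized by arm (SAP 12.2). All values are listed, and no inferential safety analysis is planned. This stands: individual cases are not lost. It does not repair the counts, and adverse event reporting depends on the investigator's judgement of significance.

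**A worst-value table has its own bias.** If one arm is tested more often because of symptoms, it has more chances to cross a threshold. This is right, and is why the by-visit tables should stay alongside.

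**Stronger readings to avoid.**
- A reader might infer that abnormal values are always dropped or overwritten. They are not: a value counts if it is the closest or only one in its window, and even a repeat within 2 days leaves the first value in place on 6 of 11 visit days.
- A reader might extend the point to vital signs, since Protocol 3.3.2.2 says "Vital signs should also be assessed in the case of abnormal clinical signs and symptoms". SAP 12.6.3 plans only descriptive summaries of them, with no outlier count or shift table.
- SpO2 categories are tied to time points of each walk test (SAP 12.3), so little is lost there.
- A post-dose reading on Day 1 also falls in no window, but the visit schedule plans no such measurement.

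**Conclusion.** The point holds in a bounded form. As written, the rule reaches the laboratory shift tables and ECG abnormality counts and, by inference, the QTc counts. With a Week 16 ECG in window, an unscheduled ECG on Days 2 to 107 never counts. An abnormal laboratory value taken before the target day can be replaced by a repeat at least as close to it (5 of 11 visit days for a repeat 1 or 2 days later, 2 of 11 at 7 days). Laboratory and PFT values on Days 72 to 99 are excluded outright.

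The consequence is under-counting in between-arm safety tables, relative to counts of any on-treatment abnormality. A reader might wish to turn the fractions into a percentage of abnormal results lost, or to conclude that a difference between arms is diluted. The documents support neither: they do not say how often tests are repeated, how often repeats are normal, or whether this differs by arm. Nor are the by-visit tables wrong for by-visit questions. The primary analysis is untouched. The change is worth making because it is cheap and these are the tables used to compare safety.

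**What to change.** - **SAP 8.6:** state that the closest-to-target rule applies to efficacy data and to by-visit summaries.
- **SAP 12.4 and 12.6.1:** state that the FEV1 count and the QTc category counts use all on-treatment values after the first dose, scheduled or unscheduled, including PFT values on Days 72 to 99.
- **SAP 12.5.1 and 12.5.2:** add a worst on-treatment row or column to the shift tables, on the same basis and including Days 72 to 99. Take lowest and highest separately where both directions matter.
- Define the on-treatment period used for these counts.
- Keep the by-visit tables, and footnote that worst-value counts depend on how often each arm is tested.
- Leave the vital-sign and SpO2 tables as they are.

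The cost is SAP wording and one or two derived records per parameter, with no change to trial conduct. The downsides are counts somewhat higher in both arms, spurious first results that stay in the count (these can be footnoted), and sensitivity to unequal testing. The text should be settled before unblinding.

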8 STUDY TERMINATION

8.1 CRITERIA FOR SUBJECT WITHDRAWAL

A subject may voluntarily withdraw or be withdrawn from the study and/or study drug by the Investigator at any time for reasons including, but not limited to, the following:

- The subject wishes to withdraw from further participation.
- A serious or life-threatening AE occurs or the Investigator considers that it is necessary to discontinue study drug to protect the safety of the subject.
- The subject consistently deviated from the protocol.
- Lung transplantation.
- The subject becomes pregnant.
- The subject's behavior is likely to undermine the validity of his/her results.

If a subject is discontinued from the study prematurely, the Investigator must provide an explanation in the eCRF and complete the End of Study Record for that subject. If study drug has been administered, the Investigator should make every effort to perform all scheduled evaluations prior to discharge. In the event that a subject discontinues study drug prematurely due to an AE, the subject will be followed until either the Investigator determines that the AE has resolved, it is no longer considered clinically significant, the subject is lost to further follow-up, or for 30 days if the AE extends beyond the final visit.

If a subject discontinues study drug prematurely for any reason, the subject should be encouraged to remain in the study and attend the remaining scheduled study visits (excluding the Week 15 Visit) up to and including Week 16.

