10.3.4 Safety Analyses

The safety of inhaled treprostinil will be evaluated by comparison of the following parameters between the 2 treatment groups:

- 1. AEs
- 2. Oxygenation
 - a. Pulse oximetry (SpO₂)
 - b. Supplemental oxygen (L/min) requirement
- 3. Pulmonary function:
 - a. FEV1
 - b. FVC
 - c. TLC
 - d. DLCO
- 4. Clinical laboratory parameters
- 5. Vital signs
- 6. 12-Lead ECG
- 7. Hospitalization due to cardiopulmonary indications
- 8. Exacerbations of underlying lung disease; defined as an acute, clinically significant, respiratory deterioration characterized by evidence of new widespread alveolar abnormality

All AEs as recorded by the Investigators will be assigned a Medical Dictionary for Regulatory Activities (MedDRA) preferred term and system organ class by the Sponsor for reporting purposes. The summary of AEs will include the number and percentage of subjects, as well as the number of events reported for each preferred term. No inferential analyses are planned for the AEs.

Data collected prior to dosing will serve as Baseline values for the evaluation of data collected during the Treatment Phase. Summary statistics will be calculated for measured values and changes from Baseline values. Treatment-emergent changes in vital signs, ECGs, PFTs, oxygenation parameters, and clinical laboratory parameters will be summarized by treatment group. Incidence of hospitalization due to cardiopulmonary indications and exacerbations of underlying lung disease will be summarized by treatment group. No inferential analyses are planned on these safety endpoints.

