### 8.3 PREMATURE DISCONTINUATION AND MISSING DATA

#### 8.3.1 Missing Data Handling for 6MWD

For the analysis of 6MWD, subjects may not have completed the treatment with study drug prior to the Week 16 visit for the following reasons: death, progressive disease, AE, withdrawal of consent by the subject, protocol violation, loss to follow-up, termination of study by the sponsor, or withdrawal for other reasons. Every attempt must be made to perform all efficacy assessments immediately prior to premature termination of study drug or withdrawal from the study. In addition, subjects still receiving study drug may be too critically ill to perform the 6MWT, resulting in missing data for that assessment.

Every effort should be made to complete all scheduled study assessments for all randomized subjects. Although attempts will be made to continue to collect data after termination of study drug, these data are being collected for sensitivity analyses and descriptive purposes only. Assessments performed after treatment unblinding or more than 24 hours after the last dose of study drug will not be included in the main analyses of peak 6MWD.

For subjects whose peak 6MWD measures at Week 4, Week 8, Week 12, or Week 16 are missing, the missing value will be imputed as described in Table 8-1.

Reason for missing 6MWD measure	Imputation
Death (all causes)	Worst score (0 meters)
Clinical worsening event	Worst score (0 meters)
Too ill to perform 6MWT	Worst score (0 meters)
All other reasons	Last (peak) Observation Carried Forward (LOCF)

Table 8-1Imputation Rules for Peak 6MWD

Abbreviations: 6MWD, 6-Minute Walk Distance; 6MWT, 6-Minute Walk Test.

For subjects whose trough 6MWD measures at Week 15 are missing, the missing values will be imputed as described in Table 8-2.

Reason for missing 6MWD measure	Imputation
Death (all causes)	Worst score (0 meters)
Clinical worsening	Worst score (0 meters)
Too ill to perform 6MWT	Worst score (0 meters)
All other reasons	Baseline Observation Carried Forward (BOCF)

Table 8-2Imputation Rules for Trough 6MWD

Abbreviations: 6MWD, 6-Minute Walk Distance; 6MWT, 6-Minute Walk Test, BOCF, Baseline observation carried forward.

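### For subjects who stop drug early but stay in the study, the SAP 8.6 window rule can replace the on-drug termination value with a later off-drug one in the safety summaries, almost always so for ECG

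*SAP*

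**What the plan says.** **Visits.** Under Protocol 3.2 (schedule, footnotes s and t) and 7.6, a subject who stops drug early has a termination visit with ECG, labs, PFTs, vital signs and pulse oximetry. It is held before stopping if possible, or otherwise as close as possible to the last dose. Protocol 8.1 adds that "the subject should be encouraged to remain in the study and attend the remaining scheduled study visits" up to Week 16, apart from Week 15.

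**Windows.** SAP 8.6 states: "In order to allow slotting of discontinuation visits and visits outside the planned schedule, the visit windows have been expanded for analysis purposes". Table 8-4 then gives:
- ECG: one post-baseline window, every day after Day 1, target Day 113.
- Labs and PFTs: Days 2-71 (target 57) and Day 100 onward (target 113).
- Vital signs and pulse oximetry: Days 2-43, 44-71, 72-99 and 100 onward (targets 29, 57, 85, 113), plus a nominal Week 15.

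**Choice within a window.** With several valid observations, "only 1 of these observations will be used for summary statistics and analyses". The first criterion is "The observation closest to the target study day", and ties go to the later value. The only on-treatment condition in this section concerns values carried forward by LOCF.

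**Off-drug data.** SAP 8.3.1 says that 6MWD assessments made after unblinding or "more than 24 hours after the last dose of study drug will not be included in the main analyses of peak 6MWD". SAP section 12 restricts safety analyses to the Safety population and sets no limit by time on drug.

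**Purpose.** Protocol 10.3.4: "Treatment-emergent changes in vital signs, ECGs, PFTs, oxygenation parameters, and clinical laboratory parameters will be summarized by treatment group".

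**QTc categories.** SAP 12.6.1 reports the number and "percent of subjects with changes from Screening of <30 msec, 30 to <60 msec" and above. Protocol 3.2 and 3.3.2.3 schedule ECGs at Baseline and at Week 16 or early termination only.

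**The concern.** A subject who stops drug and keeps attending contributes on-drug and off-drug values to the same safety tables. The on-drug termination value bears most directly on what the drug was doing when it was stopped, but the selection rule looks only at distance from the target day. A value taken weeks after the last dose can stand in its place and be summarised as treatment-emergent change in the assigned arm. The tables exposed are the by-visit summaries, the laboratory shift tables, the SpO2 bands and the QTc counts. The QTc-change categories have a separate fault: their reference visit has no scheduled ECG unless Screening and Baseline are combined.

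**Working it through.** **1. The plan's own figure.** It serves here only to size the group of early stoppers. With a difference of 30 m, SD 75 m, two-sided alpha 0.05 and 90% power, n per arm = 2 × (1.960 + 1.282)² × (75/30)² = 131.4, so 132. At the planned 133 per arm, power is 90.4% (normal) or 90.1% (t). Then 133/0.85 = 156.5, so 157 per arm and 314 in total. The plan's 266 and 314 are reproduced. The discontinuation allowance is 0.15 × 314 = 47.1 subjects.

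**2. Single cases, scheduled visits on target.**
- ECG, stop on Day 29: the termination ECG is |29 − 113| = 84 days from target and the off-drug Week 16 ECG is 0 days. The off-drug value is used.
- Labs, stop on Day 50: |50 − 57| = 7 days against 0 for the off-drug Week 8 visit. The off-drug value is used.
- Labs, stop on Day 60: |60 − 57| = 3 days against 0 for the Week 8 visit, which was on drug. An on-drug value is used.

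**3. Every possible stop day.** Table 8-4 and the hierarchy were applied to termination on each of Days 2-112 (111 days), assuming the subject attends the remaining visits. Visits were placed on target, then all 5 days early or all 5 days late, the limits of the protocol window. The table gives the days on which an off-drug value displaces the termination value.

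| Data | On target | 5 days early | 5 days late |
|---|---|---|---|
| ECG | 111/111 (100%) | 106/111 (95.5%) | 107/111 (96.4%) |
| Labs, PFTs | 68/111 (61.3%) | 58/111 (52.3%) | 60/111 (54.1%) |
| Vital signs, SpO2 | 66/111 (59.5%) | 46/111 (41.4%) | 50/111 (45.0%) |

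On target, the lab/PFT days are 2-56 and 100-112 (55 + 13 = 68). The vital sign/SpO2 days are 2-28, 44-56, 72-84 and 100-112 (27 + 13 + 13 + 13 = 66). These are shares of calendar days, not of subjects.

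The ECG exceptions lie at the end of treatment. If Week 16 is held on Day 118, a termination ECG on Days 109-112 is closer to Day 113 and is kept. Counting on to Day 117 in that case gives 107/116 = 92%. If Week 16 is held on Day 108, the five remaining days fall on or after that visit.

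**4. What happens on the other days (on target).** For labs/PFTs, an earlier on-drug Week 8 value is used on Days 58-71 (14 days), the termination value is kept on Day 57, and Days 72-99 (28 days, 28/111 = 25%) belong to no window. For vital signs/SpO2, an earlier on-drug scheduled value is used on 42 days and the termination value on 3.

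**5. Two further routes.** The Day 72-99 loss comes from the gap in Table 8-4, not from the closest-day rule. Off-drug values in windows after the stop enter the tables because safety summaries have no on-treatment limit, whatever the rule within a window.

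**6. QTc reference.** The schedule shows no ECG at a separate Screening visit, and Table 8-4 has only Baseline and Week 16 for ECG. A change from Screening therefore has no scheduled reference unless the two visits are combined.

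**The case against.** A reader might infer that the on-drug value is always discarded and that the tables are therefore biased toward no harm. The documents do not support that, for these reasons:

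- **Scope.** Only for ECG is displacement nearly universal, and even there it is not absolute. For the other data it depends on the stop day, and on many days an on-drug value is kept.
- **Not lost altogether.** Unselected values stay in the listings, flagged (SAP 8). Clinically significant laboratory values and test changes are reported as AEs (Protocol 3.3.2.4, Appendix 15.2), and AE summaries are not windowed. The count of FEV1 falls above 20% is already defined over any post-Baseline visit (SAP 12.4). No inferential tests are planned on these safety endpoints.
- **Direction.** Under Protocol 7.8, subjects who stop for treatment-related AEs cannot enter the open-label study even if they complete every visit, so they lack that incentive to stay. Clinical-worsening stoppers have it, and their later off-drug values could be worse rather than recovered.
- **Numbers.** The 15% is a sample-size allowance for discontinuation. It is not a rate of stopping drug while remaining in the study.
- **QTc.** SAP 12.6.1 also summarises ECG at Baseline with changes at Week 16, so Screening is most likely a wording slip.

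All of this stands and limits the point. It does not supply an on-treatment rule for the safety summaries, and AE reporting and listings do not repair the QTc, shift and SpO2 tables.

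**Conclusion.** The point holds in limited form. SAP 8.6 can put an off-drug value in place of the on-drug termination value, and for ECG it does so on about 95-100% of stop days from Day 2 to Day 112. For the other data the share is about 60% with visits on target and 41-54% with visits shifted 5 days. A further 28 stop days leave lab and PFT termination values outside every window. The shares assume that the subject attends all remaining visits except Week 15.

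The number of subjects cannot be derived from the documents. As an illustration only, if the 15% allowance (47 subjects) were all drug stoppers and 30-70% of them stayed, 14-33 subjects would be exposed (0.30 × 47 = 14.1; 0.70 × 47 = 32.9). The retention range is an assumption. Bias toward no harm is possible but not established. This should be corrected before unblinding, as a matter of descriptive safety reporting; it does not affect the primary analysis.

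**What to change.** In SAP 8.6, for ECG, labs, PFTs, vital signs and pulse oximetry:
1. Within a window, give an on-drug observation precedence over a later off-drug one. Treat the premature-termination visit as on drug even if it was held shortly after the last dose. A strict 24-hour limit borrowed from 8.3.1 could remove the very visits the rule should protect, since the protocol allows them after the last dose.
2. Summarise off-drug values separately.
3. Assign lab and PFT termination visits on Days 72-99 to a window or to their own row.

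In SAP 12.6.1:

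4. Base the QTc ≥500 msec and QTc-change counts on any on-drug post-Baseline ECG, including the termination ECG.
5. Take the QTc-change categories from Baseline instead of Screening.

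The cost is SAP wording and an on-drug flag built from dosing dates already collected. Late-visit denominators become smaller and one extra table is produced. The Week 16 ECG row would include termination ECGs from earlier days, as Table 8-4 already provides for subjects who leave the study.
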